## Analysis Plan

### Statistical Considerations:

*Data Management:* Data forms collected will be converted to equivalent electronic data entry forms with use of REDCap. REDCap (Research Electronic Data Capture) is a secure, web-based application designed to support data capture for research studies, providing: 1) an intuitive interface for validated data entry; 2) audit trails for tracking data manipulation and export procedures; 3) automated export procedures for seamless data downloads to common statistical packages; and 4) procedures for importing data from external sources. REDCap is hosted on secure servers located in the Loyola Medical School Campus and supported by the IT department. Project staff will be trained in the use of REDCap for entry of study data. Appropriate logic and limits checking (including cross-form validity checks) will be implemented in REDCap to facilitate accurate and consistent data entry. Study information within the virtual environment will be available for participant tracking activities such as production of result and reminder letters, scheduling of interim telephone contacts, and scheduling and tracking of follow-up visits.

*Statistical Analysis:* It has been argued that the current rate of wound complication is about 10%. We postulate that patients following this treatment will experience a lower rate of wound complication. The incidence of infection will be estimated as the proportion of patients who developed infection by the end of the study period. Confounded-adjusted rates will be estimated using generalized linear models (identity link, binomial family). We will apply a one-sample, two-sided, 5% significance Z-test to compare the rate of infection with the new treatment to the historical 10%.

In addition, comparisons between the silver dressing group and the contemporary comparison group will be made by T-test, Chi-square, Fishers exact test, logistic regression modeling.

[figure not shown]
*Sample Size/Power Justification:* As stated above, we are interested in demonstrating that the rate of wound complication is lower than the historical 10% value found in the literature. We will accrue **185 patients** to detect a 5% difference (10% vs 5%) using the one-sample Z-test with 80% statistical power. Testing via the generalized linear model to adjust for confounders will increase the statistical power to detect differences.

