## **The Role of Adherent Occlusive Antimicrobial Absorbent Foam Dressing in Prevention of Cesarean Section Wound Complications**

### **Background and Significance:**

Cesarean delivery rates continue to increase in the United States, accounting for 33% of all births in 2011 (1). Patients undergoing cesarean delivery are at a greater risk of postpartum infection when compared to vaginal delivery. Additionally, the most prominent risk factor for postpartum infection is cesarean delivery. The spectrum of puerperal infections ranges from surgical site infections (SSI), endometritis, and abscess to pelvic thrombophlebitis, bacteremia, and sepsis (2). 2.5-16% wound complication post csection which includes seroma, hematoma, infection, separation and dehiscence. Risk factors for wound complication include medical disorders such as diabetes, tobacco use, preeclampsia, obesity, frequent vaginal exams, internal monitoring and emergent cesarean. (3) Reported rates of post-cesarean wound infection range from 2.71-11.4% (4-8). Risk factors for post-cesarean SSIs include prolonged operating time, body mass index (BMI) greater than 30, and increased thickness of subcutaneous tissue (5,6). Furthermore, patients undergoing cesarean delivery experience increased risk of rehospitalization within 30 days postpartum, as the majority of SSIs become apparent following discharge (9, 10). SSI is the principal reason for readmission following cesarean delivery (9).

Wound infection is an economic and social burden to the health care system. Of the major health care-associated infections—central line-associated bloodstream infection, ventilator-associated pneumonia, SSI, Clostridium difficile infection, and catheter-associated urinary tract infection—SSI contributes the most to the total annual cost of health care-associated infections (11,12).

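### The identity-link binomial model for adjusted rates has about 9 expected events, no named covariates and no fallback; it often reaches zero or negative fitted risks and should give way to standardised logistic regression

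*Combined protocol and SAP*

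**What the plan says.** All of this is in the combined protocol and SAP, mostly under Statistical Considerations.

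- Adjusted estimation: "Confounded-adjusted rates will be estimated using generalized linear models (identity link, binomial family".
- The same model is also meant for inference: "Testing via the generalized linear model to adjust for confounders will increase the statistical power to detect differences".
- The named test is unadjusted: "We will apply a one-sample, two-sided, 5% significance Z-test to compare the rate of infection with the new treatment to the historical 10" per cent.
- The contemporary group has a separate list of methods: "comparisons between the silver dressing group and the contemporary comparison group will be made by T-test, Chi-square, Fishers exact test, logistic regression modeling".
- The design is 185 women, "to detect a 5% difference (10% vs 5%) using the one-sample Z-test with 80% statistical power".

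The plan does not list the confounders, their number or their coding. It does not say whether the adjusted model covers the dressing group alone or both groups, which adjusted rate will be reported (at mean covariates, for a reference profile, or averaged over women), or what happens if the model fails. The Background names candidate factors: "Risk factors for wound complication include medical disorders such as diabetes, tobacco use, preeclampsia, obesity, frequent vaginal exams, internal monitoring and emergent cesarean", and "Risk factors for post-cesarean SSIs include prolonged operating time, body mass index (BMI) greater than 30, and increased thickness of subcutaneous tissue".

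**The concern.** With an identity link, risk is a straight line in the covariates and nothing stops it crossing zero. At a 5% event rate most women sit close to that boundary. Where a fitted risk is zero or negative the binomial likelihood is undefined, so software either fails to converge or holds the fit at the edge, and the answer can depend on the program used.

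The trial will have one data set. Without named covariates or a fallback, the analyst would choose a rescue model after seeing the results. The quantities at stake are the adjusted rates and any adjusted comparison with the contemporary group, which is the only comparison in the plan for which covariates on both sides could exist.

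**Working it through.** **1. The plan's own figure.** For a one-sample Z-test, n = [z_α√(p0·q0) + z_β√(p1·q1)]² / (p0 − p1)², with p0 = 0.10, p1 = 0.05 and 80% power.

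- Two-sided 5%: (1.960 × 0.300 + 0.842 × 0.218)² / 0.0025 = 238.03, so 239. Power at 185 is about 66%.
- One-sided 5%: (1.645 × 0.300 + 0.842 × 0.218)² / 0.0025 = 183.3, so 184.

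The planned 185 therefore matches a one-sided test although the text says two-sided. That is a separate point; 185 is taken as given below.

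**2. Expected events.** 185 × 0.05 = 9.25 at the design rate; 185 × 0.10 = 18.5 at the historical rate.

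**3. Why the line crosses zero.** Assume mean BMI 32, range 18–60, and log-odds 0.07 per BMI unit. Near a 5% risk the slope is about 0.07 × 0.05 × 0.95 = 0.0033 per unit, so the line reaches zero about 0.05 / 0.0033 = 15 units below the mean, near BMI 17. That is at the edge of the data, and with about 9 events modest sampling error in the slope tips it over.

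**4. How often it happens.** All covariate distributions and effects are assumptions; true risks were logistic.

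- Set A (400–500 data sets per setting): BMI mean 32, SD 7, clipped to 18–60, log-odds 0.07 per unit; diabetes 12%, smoking 10%, preeclampsia 12%, with log-odds 0.6, 0.5, 0.4.
- Set B (150 data sets per setting, Monte Carlo error about 4 points): obesity 50%; diabetes, tobacco and preeclampsia 10% each; emergent cesarean 30%; BMI mean 32, SD 6.5; age mean 29, SD 6; odds ratios 1 to 2.

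Share of fits with n = 185 in which at least one fitted risk is at or below zero (set A), or in which the constrained fit reaches the zero bound (set B):

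| Covariates | 5% rate | 10% rate |
|---|---|---|
| A: BMI coded >30 | 11% | 0.5% |
| A: BMI >30 and diabetes | 38% | 13% |
| A: continuous BMI | 51–57% | 35–45% |
| A: continuous BMI + 3 binary | 92–94% | 75–78% |
| B: one or two binary | 3–32% | 0–11% |
| B: continuous BMI (no effect to effect) | 31–56% | 11–34% |
| B: three binary | 57–69% | 30–39% |
| B: five or six covariates | 89–95% | 65–95% |

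Non-convergence was 4–10% under set A with the dressing group alone, 3–9% under set B with three to five covariates, and about 4–12% over all settings.

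**5. Effect on the dressing-group adjusted rate.** Set B, 5% rate, 400 data sets in each of four scenarios:

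- The rate at mean covariates averaged 0.050. Coverage of the 95% interval was 93–95%, against 95–96% for the crude Wald interval. Set A gave 89–93%, with 87% in one run at a 10% rate with continuous BMI.
- Among fits with some risk at or below zero, the median gap from the crude rate was at most 0.0002. The largest gaps were 0.03 (five binary factors) and 0.14 (BMI plus four binary).
- The interval for the reference profile extended below zero in 28–74% of data sets.

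**6. Effect on an adjusted risk difference.** Set A, 185 dressing women at 5% pooled with 185–370 comparison women at 10%, true difference −0.05:

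| Method | Mean estimate | Note |
|---|---|---|
| Identity-link coefficient | −0.035 to −0.043 | interval coverage 73–78% |
| Logistic regression, predicted risks averaged | −0.047 to −0.050 | no failed fits |

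The identity-link shortfall is 0.007 to 0.015, or 14% to 30% of the true difference. With 400 data sets the standard error of a coverage near 75% is √(0.75 × 0.25 / 400) = 0.022, so allow about 4 points either way. Part of the shortfall arises because the fit gives most weight to low-risk women, whose absolute difference is smallest when the true model is logistic.

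**7. Check on the replacement.** Plain Firth penalisation converged in all 1,600 fits tried but raised the average risk: 6.0–6.1% against a crude 5.0% in the dressing group alone, and 5.5% against 4.9% when pooled. The risk difference was nearly unaffected (5.1 points). Ordinary logistic regression on the dressing group alone with three to five covariates had all coefficients of moderate size in only 36–64% of data sets, a sign of separation, although its average predicted risk stayed at 0.050–0.051.

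**The case against.** The strongest case against has five parts.

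- *The frequency depends on assumed covariates.* This stands. The plan names none, and one Background list gives BMI as a threshold at 30, which is binary. With one or two binary factors, boundary fits are a minority.
- *The adjusted rate itself is mostly sound.* This stands for the dressing group at mean covariates. A reader might infer that the adjusted estimates and intervals are unreliable across the board; step 5 does not support that. But the plan does not say which adjusted rate it will report, so the well-behaved summary cannot be presumed.
- *The primary result is untouched.* This stands. A reader might infer that the main conclusion rests on this model, but the primary estimate is a simple proportion and its test is an unadjusted Z-test. The model does carry weight beyond description, because the plan also assigns it a testing role.
- *The plan lists logistic regression for the contemporary comparison.* This is true, so the poor coverage in step 6 applies only if the stated adjusted-rate model is fitted to both groups. The text neither says so nor rules it out. The size of that group is not given, so 185–370 is an assumption.
- *The simulated truth was logistic, which favours logistic regression.* This is fair: if absolute differences were constant across women, the shortfall in step 6 would be smaller. The boundary problem would remain, because it comes from few events near zero.

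**Conclusion.** The concern holds in a limited form. As written, the adjusted analysis uses a model that often breaks its own range at this event rate once BMI with an effect enters as continuous or three or more binary factors enter, and the plan has no rule for that case. It is more than a missing detail: fitted to both groups, the stated model gave intervals that missed the true difference about a quarter of the time (coverage 73–78%).

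The damage falls on profile-specific risks, on occasional fits that fail or go far astray, and on an adjusted difference against the contemporary group. It does not extend to the unadjusted primary test, nor usually to the dressing group's average adjusted rate. The percentages rest on assumed covariate distributions, effects and comparison-group size. It should be corrected before analysis, but it does not by itself invalidate the trial.

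**What to change.** In the Statistical Analysis paragraph:

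1. Replace the identity-link model with logistic regression fitted to the dressing and contemporary groups together.
2. Name a short covariate set in advance, with coding, limited to variables available in both groups. Expected pooled events at the rates above are 9.25 + 18.5 = about 28 with 185 comparison women, or 9.25 + 37 = about 46 with 370, which supports only a few covariates.
3. Average the predicted risks over all women under each dressing to obtain adjusted risks and the adjusted risk difference, with a bootstrap 95% interval.
4. State in advance that, if events prove too sparse, an intercept-corrected Firth fit will be used. Plain Firth should not be used for the rates, because it inflates the average risk.
5. Report the dressing group's rate against 10% unadjusted. The plan has no historical covariate data, so there is nothing to adjust that benchmark to.

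The cost is SAP wording and one extra computing step, since the risk difference is no longer read from a coefficient. The real limit is data: for non-participants the protocol mentions only demographic and outcome data, and Study Flow and Measurements lists BMI under examination, not demographics. The sponsor should confirm which covariates exist in both groups before naming the set.

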Evidence to support the use of silver-containing dressings to limit and treat post-cesarean SSIs is particularly limited. Connery et al. (2012) conducted a retrospective review to evaluate the effectiveness of silver-containing dressings versus traditional wound dressings in reducing additional postoperative visits associated with SSIs in patients undergoing cesarean delivery. Although they did not find a significant difference between the experimental and control groups, the study was limited due to small number of study subjects and a higher number of medical comorbidities in the study group (21).

Despite measures to decrease the risk of postpartum infection following cesarean delivery, the rate of SSI remains prominent. Wound infections are responsible for longer hospital stays, readmissions, and ultimately, increased costs to the healthcare system. Silver-containing dressings may prevent wound infection. The purpose of the current study is to determine if the use of a silver-impregnated dressing decreases the incidence of SSI following cesarean delivery.

**Purpose:** To investigate the role of an adherent soft silicone anti-microbial occlusive foam silver-impregnated dressing for primary cesarean delivery.

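### The only powered test compares the dressing group with a fixed 10%, which cannot by itself show that the dressing lowers complications; the planned concurrent comparison should carry any such statement

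*Combined protocol and SAP*

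**What the plan says.** The Background and Significance section gives the study's purpose as to "determine if the use of a silver-impregnated dressing decreases the incidence of SSI following cesarean delivery". Primary Aim 1 is narrower: it asks only for the complication rate with the dressing.

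Under Statistical Considerations the reference rate is introduced with "It has been argued that the current rate of wound complication is about 10"%. The test is then stated: "We will apply a one-sample, two-sided, 5% significance Z-test to compare the rate of infection with the new treatment to the historical 10"%. The sample-size paragraph aims to show a rate "lower than the historical 10% value found in the literature", with 185 patients for 10% against 5% at 80% power.

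Two further analyses are named. One is a model: "Confounded-adjusted rates will be estimated using generalized linear models (identity link, binomial family"). It has no group term, comparator or covariates. The other is introduced as an addition: "comparisons between the silver dressing group and the contemporary comparison group will be made by T-test, Chi-square, Fishers exact test, logistic regression modeling". No outcome, covariates, effect measure or priority are given for it. Methodology of Measurements describes the comparison group as same-period women with the same type of incision and closure who did not take part.

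The Background gives two literature ranges: "2.5-16% wound complication post csection which includes seroma, hematoma, infection, separation and dehiscence", and "Reported rates of post-cesarean wound infection range from 2.71-11.4"%. Methodology of Measurements defines the primary outcome as a composite of wound disruption and/or infection within 4 weeks.

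**The concern.** The stated purpose is comparative, but the only test with an alpha, an effect size and a sample size has no comparator. It treats 10% as the known untreated rate. If that rate is really lower at this hospital, under these eligibility rules and this outcome definition, an ineffective dressing can be credited with a benefit. If it is higher, a real benefit can be missed. The documents point both ways: the population is called high risk and small skin defects count as events, but women with intrapartum fever are excluded.

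The wording of the test adds a bias in one direction. Infection is one component of the composite, so its rate cannot exceed the composite's. Testing infection alone against a benchmark for all wound complications favours a finding of *lower*, whatever the dressing does.

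**Working it through.** **Inputs.** From Statistical Considerations: n = 185, p0 = 10%, p1 = 5%, two-sided 5%, 80% power. From the Background: 2.5–16% and 2.71–11.4%. The individual untreated rates below are assumptions within those ranges. The size of the comparison group is also assumed, because the documents give none.

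**The plan's own figure.** n = [(z_α√(p0(1−p0)) + z_power√(p1(1−p1))) / (p0−p1)]².

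- Two-sided: [(1.960×0.300 + 0.842×0.218)/0.05]² = 238.03, so 239.
- One-sided: [(1.645×0.300 + 0.842×0.218)/0.05]² = 183.3, so 184.

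By this formula 185 fits a one-sided test, not the two-sided one stated. That is a separate matter; the results below use n = 185 and the stated two-sided test.

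**Rejection region.** The plan does not say which variance the Z-test uses, so both are shown.

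- Null variance: 0.10 − 1.960×√(0.09/185) = 0.0568. Since 0.0568×185 = 10.5, *lower* is declared at 10 or fewer events.
- Sample variance: 11 events give z = −2.33 and 12 give z = −1.94, so *lower* is declared at 11 or fewer.

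**Probability of declaring *lower*** = P(X ≤ 10) or P(X ≤ 11), with X binomial (185, true rate with the dressing):

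| True rate with the dressing | Null variance | Sample variance |
|---|---|---|
| 5% | 68% | 78% |
| 6% | 44% | 57% |
| 7% | 25% | 35% |
| 8% | 12% | 19% |
| 10% | 1.9% | 3.6% |

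The test depends only on the rate with the dressing, so each row has more than one reading.

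- If the dressing does nothing, the 6%, 7% and 8% rows are the chance of false credit at those untreated rates.
- If the dressing halves a 16% rate, the 8% row applies: a large benefit is detected 12% or 19% of the time.
- If the composite rate is 10%, an assumed 7% of women have infection and the dressing does nothing, testing infection alone declares *lower* 25% or 35% of the time.

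**The concurrent comparison (unadjusted pooled two-group Z-test, two-sided 5%).**

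- Inert dressing, equal underlying rates between 5% and 16%, 185 v 185: *lower* is declared 2.4–2.6% of the time (exact).
- Inert dressing, assumed underlying rates of 8% in participants v 10% in non-participants: 9.8%. At 7% v 10%: 17.6%.
- Power for 10% v 5% (normal approximation): about 45% with 185 comparison women and 56% with 555.
- Expected 95% interval at 185 each: −5 ± 1.96×√(0.0475/185 + 0.09/185) = −5 ± 5.3 points, or about −10.3 to +0.3.

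**The case against.** The strongest reply has three parts.

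First, the Z-test is valid for the question it poses. The sample-size paragraph words the claim as a comparison with a literature value, the study is called observational, and Primary Aim 1 is descriptive. This stands: the test is not wrong, and the aim of estimating the rate is unaffected. The difficulty arises only if the result is used to answer the Background's question. That use is likely, because the plan also postulates that the treatment will lower the rate and nominates no other result to answer it.

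Second, a reader might infer that the plan has no model-based concurrent comparison, since the identity-link model names no comparator. The documents do not support that. Logistic regression is itself a binomial generalised linear model, and the plan lists it for the dressing and contemporary groups. What is missing is narrower: its outcome, covariates, effect measure and priority. Choosing the identity link over logistic regression is a matter of preference.

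Third, a reader might infer that a concurrent comparison would hold the false-benefit rate near 2.5%. That holds only if participants and non-participants have the same underlying risk, and nothing in the documents shows they do. With modest differences the error is about 10% or 18%, against 12–19% or 25–35% for the benchmark test at the same participant rates. The gain is real but limited.

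The mismatch between infection and the composite may be loose terminology, since the primary outcome is itself labelled SSI. As written, though, it is a different test.

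**Conclusion.** The point holds in limited form. Beating a fixed 10% does not by itself show that the dressing reduces complications, and the plan does not say that its concurrent comparison, rather than this test, would support such a statement. At untreated rates of 6–8%, inside both published ranges, an inert dressing is declared *lower* between 12% and 57% of the time, depending on the rate and the variance form. On the composite range a halving from 16% is usually missed. These figures rest on assumed untreated rates, n = 185 and exact binomial probabilities; the documents give no local rate.

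This should be changed, but it does not undermine the study: the descriptive aim survives and the Z-test can stay as a benchmark. The documents do not support the view that the concurrent comparison would settle causation.

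**What to change.** 1. In the Z-test sentence, replace the rate of infection with the composite primary outcome within 4 weeks, and state the variance form. Report the rate with its 95% CI. Add: *This test compares the rate with a 10% benchmark and does not by itself show that the dressing lowers complications.*
2. Rest any statement that the dressing lowers complications on the planned adjusted comparison with the contemporary group. Report an adjusted risk difference with 95% CI for the same composite and window, either by standardisation from the logistic model or from the identity-link model fitted to both groups. Apply the protocol's exclusion criteria, including intrapartum fever, to the comparison women, and fix a short covariate list before outcomes are compared.
3. If fever status, event timing or comparable ascertainment cannot be confirmed in the comparison data, draw no effectiveness conclusion. If outcomes were compared before covariates were fixed, say so and label the result exploratory.

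**Cost.** Changed wording, one model fit and a check of what the deidentified comparison data contain; no new patients. The check could fail. The protocol describes those data only as demographic and outcome data. Events must also be datable to 4 weeks although scheduled visits fall at 7 days and 6 weeks, and early wound inspection may differ because the two dressings come off at different times. Residual confounding will remain because the comparison women are non-randomised non-participants. With power of about 45–56% at the assumed group sizes, report the comparison as an estimate without a power claim.

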Obstetric physicians will perform a standardized physical examination of the wound dressing on each postoperative day, at 7 days post-operatively on dressing removal, and the wound will be examined also at the standard 6 weeks postpartum examination for patients in both groups. For patients who do not return for their postpartum visit at 7 days and 6 weeks, a standardized phone evaluation will be conducted by trained study personnel; any report of wound complication will be documented in the medical record.

The **primary outcome variable** will be a composite of wound disruption and/or infection occurring within 4 weeks postoperative (**wound complication rate: SSI**). Wound disruption will be defined as any separation of the wound (ranging from small skin defects to entire separation of the wound) and subcutaneous skin dehiscence, i.e. from seroma or hematoma. Wound infection will be classified by the Centers for Disease Control and Prevention (CDC) guidelines (22). **Secondary outcomes will include:** pain measured at 24h, 48 h, 7 days at dressing removal, and 6 weeks after cesarean delivery using a ten-point visual analog scale (VAS) from 0 to 10 (with 0 indicating no pain and 10 indicating worst conceivable pain), cosmesis score (as defined by the Stony Brook Scar Evaluation Scale (23)) 7 days and 6 weeks postoperatively, mobility assessment, readmission to the hospital, post discharge fever or antibiotic therapy, and additional clinic visits (both routine and unscheduled). Please see Figures 1 and 2. Additionally, all patients will be queried on degree of satisfaction on a scale of 1-10 as will clinicians queried on ease of use.

In addition, deidentified demographic and outcome data on those who had a primary csection with transverse incision closed in a subcuticular fashion who did not participate in the silver dressing during the same time period were collected.

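### The planned estimate and Z-test count infection alone, but the primary outcome, the 10% benchmark and the sample size are for wound complication

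*Combined protocol and SAP*

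**What the plan says.** Under Methodology of Measurements, the combined protocol and SAP makes the primary outcome a "composite of wound disruption and/or infection occurring within 4 weeks postoperative". Disruption has its own definition, which reaches down to small skin defects and includes dehiscence from seroma or hematoma. Infection is classified separately by CDC guidelines. Primary Aims also refers to the wound complication rate.

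Under Statistical Considerations, three statements follow that outcome:

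- Benchmark: "It has been argued that the current rate of wound complication is about 10" per cent.
- Hypothesis: "We postulate that patients following this treatment will experience a lower rate of wound complication".
- Sample size: the aim is "demonstrating that the rate of wound complication is lower than the historical 10% value found in the literature", with 185 patients "to detect a 5% difference (10% vs 5%) using the one-sample Z-test with 80% statistical power".

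The sentences that say what will be computed do not:

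- Estimate: "The incidence of infection will be estimated as the proportion of patients who developed infection by the end of the study period".
- Adjusted rates: "Confounded-adjusted rates will be estimated using generalized linear models (identity link, binomial family"), with no outcome named.
- Test: a one-sample, two-sided, 5% Z-test to "compare the rate of infection with the new treatment to the historical 10" per cent, with no time window.

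**The concern.** Infection is one component of the composite, so an infection rate can never exceed the composite rate in the same patients. Setting the narrower count against a benchmark labelled for the wider one makes a result below 10% easier to reach, whether or not the dressing works. The study is unrandomised and this comparison with a fixed historical rate is its planned primary test, so such a result would be read as benefit. It would also not address the stated primary outcome.

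The estimate adds a second mismatch. It counts events to an end of study that is not defined, whereas the primary outcome stops at four weeks. With two readings available in the text, the choice between them could be made after the data are seen.

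**Working it through.** **Inputs from the document.** n = 185, p0 = 10%, p1 = 5%, 80% power, two-sided 5% one-sample Z-test (Statistical Considerations). Published ranges are 2.5–16% for wound complication and 2.71–11.4% for wound infection (Background and Significance). The document does not give the share of complications that are infections, so shares of 50% to 90% are assumed below.

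**The plan's own figure.** n = [(z_α√(p0(1−p0)) + z_β√(p1(1−p1)))/(p0−p1)]².

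- Two-sided 5%: [(1.960×0.300 + 0.842×0.218)/0.05]² = 238.03, so 239.
- One-sided 5% (1.645 in place of 1.960): 183.27, so 184.

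The stated 185 therefore fits a one-sided test, not the stated two-sided one. That is a separate matter and does not affect this point, but it explains why the power below is 68% rather than 80%.

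**Rejection rule at n = 185.** z = (X/185 − 0.10)/√(0.10×0.90/185), with standard error 0.02206.

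- X = 10: z = −2.083, p = 0.037, reject.
- X = 11: z = −1.838, p = 0.066, do not reject.

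A rate below 10% is declared when X ≤ 10.

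**Chance of declaring a rate below 10% with no dressing effect.** This is the exact binomial P(X ≤ 10), with infection rate = composite rate × share.

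| True composite rate | Share 50% | 60% | 70% | 80% | 90% | Composite tested |
|---|---|---|---|---|---|---|
| 10% | 68% | 44% | 25% | 12% | 5% | 1.9% |
| 12% | 44% | 22% | 8% | 3% | 1% | 0.2% |

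**Where the inflation ends.** P(X ≤ 10) falls to the nominal lower-tail 2.5% at an infection rate of 9.7%. That is a share of 97%, 81%, 69% or 61% when the true composite rate is 10%, 12%, 14% or 16%.

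**One concrete result.** Suppose 18 of 185 patients (9.7%) have a complication. The composite test gives z = −0.123, p = 0.90. The infection test rejects only if 10 or fewer of the 18 are infections, so the two tests disagree only if 8 or more are non-infectious.

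**The opposite case.** Suppose the 10% is really an infection-only rate and infection with the dressing is 5%. The infection test then declares benefit 68% of the time. For the composite test against the same 10%, take composite rate = 5%/share on the dressing, which gives 10.0%, 8.3%, 7.1%, 6.3% and 5.6% for shares of 50% to 90%. The chance of declaring benefit is 2%, 9%, 22%, 39% and 55%. This assumes that the share holds among patients wearing the dressing.

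**The case against.** The strongest reply is that this is loose vocabulary. The sample-size paragraph refers back to the analysis text and attaches the Z-test to wound complication, and Primary Aims and the primary outcome definition agree with it. The error rates above would then describe an analysis nobody meant to run. The composite is indeed the likelier intent. But usage is loose in both directions: the purpose sentence closing Background and Significance speaks only of SSI incidence, and the primary outcome is labelled as the complication rate and tagged SSI in the same phrase. Likely intent does not remove the conflict, because the two sentences an analyst would execute still say infection.

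The second reply is that the size rests on assumed shares and on what the 10% counts. That stands. Both published ranges contain 10%, so the ranges do not settle it. If the 10% counts infections only, the infection test has no inflation. At a 12% composite and a 90% share the chance is 1%, below nominal.

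The opposite-case figures also depend on their model. If the shares instead hold at baseline (infection 10%) and the dressing halves infection but leaves other disruptions unchanged, the composite rates are 15%, 11.7%, 9.3%, 7.5% and 6.1%. The chances become about 0%, 0.3%, 4%, 17% and 42%. The direction is the same.

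**Conclusion.** The concern holds and should be fixed. Confidence is high that the text contradicts itself: the outcome definition, benchmark, hypothesis and sample size concern wound complication, while the estimate and the test concern infection.

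The size of the effect is conditional. If the 10% counts non-infectious disruptions, the true composite rate is 10% and the dressing has no effect, the chance of a favourable result rises from 1.9% to between 5% and 68% for infection shares of 90% down to 50%. The gap narrows at higher composite rates and closes once the infection rate reaches 9.7%. If the 10% is instead an infection-only figure, the harm runs the other way: testing the composite against it loses power. Either way, the outcome and the benchmark must describe the same events.

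**What to change.** In the Statistical Analysis paragraph:

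1. In the estimate sentence, replace infection with the composite defined under Methodology of Measurements, and replace the end-of-study window with four weeks after surgery.
2. In the Z-test sentence, name the rate of that four-week composite.
3. In the adjusted-rate sentence, name the same outcome. It would help to do so in the comparison-group sentence too, which also names none.
4. Scheduled wound examinations go from day 7 to 6 weeks, so assign events first reported at 6 weeks or by phone to the four-week window by date of onset.
5. State which events and which time window the 10% counts.

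Infection alone can still be reported, but not as the primary test against the wound-complication benchmark.

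The cost is a few words in three or four sentences, plus onset dates for events reported after four weeks. The data forms are not in the document, so whether onset is already recorded cannot be checked. If the composite and the 10% are both kept, p0, p1 and the target number do not change on this account. If the 10% proves to be infection-only, the benchmark must change together with the outcome. The rewording makes the test match the stated outcome; it does not show that 10% is the right figure for this population.
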